5.5.4.5 Subject/Caregiver Global Impression of Change in Seizure Duration

Blinded Phase:

The SGICSD and CGICSD comprise the following questions to be rated on a 3-point scale for each seizure type:

CGICSD:

- Since the patient started treatment, please assess the average duration of the patient's seizures (comparing their condition now to their condition before treatment) using the scale below.

SGICSD:

- Since you started treatment, please assess the average duration of your seizures (comparing your condition now to your condition before treatment) using the scale below.

The 3 possible responses are:

- Decrease in average duration.
- No change in average duration.
- Increase in average duration.

The patient/caregiver will be asked to assess the average duration of seizures at Visit 3 (prior to commencement of IMP) as a memory aid for assessment further visits.

Each response will be coded with a score from 1 to 3, where 1 = Decrease in average duration, and 3 = Increase in average duration.

For each seizure type, the SGICSD and CGICSD will be summarized separately by treatment arm.

It is anticipated that only a small percentage of patients will complete the subject version of the questionnaire. Hence, no analyses will be performed for the SGICSD.

A combined score will be used as the primary analysis for this endpoint. The combined score will be defined as follows:

- If both a CGICSD and SGICSD are completed then the CGICSD will be used.
- If only a CGICSD is completed then the CGICSD will be used.
- If only a SGICSD is completed then the SGICSD will be used.

Proportional odd modelling will be carried out by including treatment arm and age group as factors. The estimated odds ratio (GWP42003-P vs. placebo), 95% CI for the odds ratio, and the p-value testing the null hypothesis that the odds ratio is equal to 1, will be presented.

Since this analysis uses a combination of caregiver and subject ratings, a sensitivity analysis will be performed using only the CGICSD score and using the same analyses as above.

Open-label Extension:

Descriptive summaries described above for the blinded phase will be repeated for OLE visits.

5.5.4.6 Vineland Adaptive Behavior Scales, Second Edition

Blinded Phase:

The Vineland-II is an individually administered instrument for assessing adaptive behaviors and consists of 4 adaptive behavior domains and a maladaptive behavior domain. The details of each domain are presented in Table 5.

Table 5 Content Description of the Vineland-II

Domains and Subdomains	Number of Items	Age Range (Years)	Content
Adaptive Behavior Domains			
Communication Domain	99	≥ 0	
Receptive	20	≥ 0	How the individual listens and pays attention, and what he or she understands
Expressive	54	≥ 0	What the individual says, how he or she uses words and sentences to gather and provide information
Written	25	≥ 3	What the individual understands about how letters make words, and what he or she reads and writes
Daily Living Skills Domain	109	≥ 0	
Personal	41	≥ 0	How the individual eats, dresses and practices personal hygiene
Domestic	24	≥ 1	What household tasks the individual performs
Community	44	≥ 1	How the individual uses time, money, the telephone, the computer and job skills
Socialization Domain	99	≥ 0	
Interpersonal Relationships	38	≥ 0	How the individual interacts with others
Play and Leisure Time	31	≥ 0	How the individual plays and uses leisure time
Coping Skills	30	≥ 1	How the individual demonstrates responsibility and sensitivity to others
Motor Skills Domain	76	≥ 0 to < 7	
Gross	40	≥ 0 to < 7	How the individual uses arms and legs for movement and coordination
Fine	36	≥ 0 to < 7	How the individual uses hands and fingers to manipulate objects
Maladaptive Behavior Domain			
Maladaptive Behavior Index	36	≥ 3	A composite of Internalizing, Externalizing, and Other types of undesirable behavior that may interfere with the individual's adaptive functioning
Internalizing (Section A)	11	≥ 3	
Externalizing (Section B)	10	≥ 3	
Other (Section C)	15	≥ 3	
Maladaptive Behavior Critical Items	14	≥ 3	More severe maladaptive behaviors that may provide clinically important information

For each subdomain, a raw score is calculated based on the responses to the individual items within the subdomain. For the maladaptive behavior index, the raw score is the sum of the 3 subdomain raw scores. Using the raw score and the patients' age the following are obtained:

- v-Scale Score: a type of standard score scale (standardized by age) to describe an individual's relative level of functioning. Ranging from a score of 1 to 24.
- 90% CI for the v-Scale Score: a range of scores that has a certain likelihood of including the individual's true score.

- Adaptive Level: a means to describe an individual's performance using terms that are nearly universal (Low, Moderately Low, Adequate, Moderately High, High).
 - For the maladaptive behavior index and maladaptive behavior subdomains the adaptive levels are: Average, Elevated or Clinically Significant.
- Age Equivalent: the age at which the raw score is average. Not applicable for the maladaptive behavior index and maladaptive behavior subdomains.

For each adaptive behavior domain, the sum of the v-scale scores of the subdomains is used along with the patients' age to obtain the following:

- Standard Score (standardized by age). Ranging from a score of 20 to 160.
- 90% CI for the domain standard score.
- Percentile Rank: the percentage of people whom the individual outperformed in his or her age group.
- Adaptive Level (Low, Moderately Low, Adequate, Moderately High, High).
- Stanine: whole number score ranging from 1 to 9 and representing a specific range of percentile ranks.

An adaptive behavior composite can then be obtained using the sum of the adaptive behavior domain standard scores (excluding the motor skills domain for patients ≥ 7 years of age). The same derived information as the adaptive behavior domain is obtained for the adaptive behavior composite.

For the maladaptive behavior index, all items within each section must be answered for a raw score to be calculated. If any of the items are missing then the maladaptive behavior index score will be missing.

For the adaptive behavior subdomains, the derivation of the raw score allows for up to 2 missing values or answers of "Don't Know" within the items used for scoring. If there are more than 2 missing values or answers of "Don't Know" then the raw score will not be calculated and the subdomain score, domain score and adaptive behavior composite score will be missing.

The adaptive levels corresponding to the v-scale scores and standard scores are presented in Table 6.

Table 6 Adaptive Levels by v-Scale Scores and Standard Scores

Adaptive Level	v-Scale Score for Subdomains and Maladaptive Behavior Index	Standard Score for Domains and Adaptive Behavior Composite
Adaptive Behavior Domains		
Low	1 to 9	20 to 70
Moderately Low	10 to 12	71 to 85
Adequate	13 to 17	86 to 114
Moderately High	18 to 20	115 to 129
High	21 to 24	130 to 160
Maladaptive Behavior Domain		
Clinically Significant	21 to 24	
Elevated	18 to 20	
Average	1 to 17	

The v-scale score from the 11 adaptive behavior subdomains, 3 maladaptive behavior subdomains and the maladaptive behavior index, and the standard score from the 4 adaptive behavior domains and the adaptive behavior composite, recorded at each visit, will be summarized, on a continuous scale, by treatment arm. The change from baseline will also be included.

The change from baseline to the end of treatment visit, for the 4 adaptive behavior domains, the adaptive behavior composite and the maladaptive behavior index only, will be analyzed using the same ANCOVA approach as specified in Section 5.5.3.2.4.

The adaptive level from the 11 adaptive behavior subdomains, 4 adaptive behavior domains, the adaptive behavior composite, the 3 maladaptive behavior subdomains and the maladaptive behavior index, recorded at each visit, will be summarized, on a categorical scale, by treatment arm.

The adaptive level from the 4 adaptive behavior domains, the adaptive behavior composite and the maladaptive behavior index only will be analyzed using ordinal logistic regression. Factors for treatment and age group will be included along with the baseline adaptive level as a covariate. The estimated odds ratios (GWP42003-P arms vs. placebo), 95% CI for the odds ratios, and the p-values testing the null hypothesis that the odds ratio is equal to 1, will be presented.

Each adaptive level for adaptive behavior will be coded with a score from 1 to 5, where 1 = Low, and 5 = High. Each adaptive level for the maladaptive behavior index will be coded with a score from 1 to 3, where 1 = Clinically Significant, and 3 = Average.

The individual responses within each domain will not be listed, only the derived information for each subdomain and domain will be listed.

Open-label Extension:

Descriptive summaries described above for the blinded phase will be repeated for OLE visits.

5.5.4.7 Wechsler Tests

Blinded Phase:

The Wechsler tests are age specific and will only be administered at a sub-group of centers that have the expertise to conduct the assessments. The age of the patient at entry is used when choosing the items to be administered. The following Wechsler Subtests will be used:

Age 2–6:

- Wechsler Preschool and Primary Scale of Intelligence – Fourth Edition (WPPSI-4) Vocabulary and Matrix Reasoning

Age 6–Adult:

- Wechsler Abbreviated Scale of Intelligence – Second Edition (WASI-2) Vocabulary and Matrix Reasoning
- Wechsler Intelligence Scale for Children – Fourth Edition (WISC-4) and Wechsler Adult Intelligence Scale - Fourth Edition (WAIS-4) Digit Span and Coding.

The T scores (Vocabulary and Matrix Reasoning), scaled scores (Coding) and forward, backward, longest forward and longest backward scores (Digit Span) will be summarized by visit including the change from baseline.

The change from baseline will be analyzed using an ANCOVA approach. The model will include baseline and stratified age group as covariates and treatment arm as fixed factor.

The estimated least squares means, treatment difference, together with the 95% CIs and p-value will be presented.

Open-label Extension:

Descriptive summaries described above for the blinded phase will be repeated for OLE visits.

5.5.4.8 Achenbach Child Behavior Checklists and Adult Behavior Checklist

Blinded Phase:

The Achenbach CBCL is a caregiver questionnaire assessing both behavioral and emotional symptoms in children. Depending on the patients' age, 1 of 2 versions of the Achenbach CBCL is used. The CBCL/1½-5 is used for children 18 months old to 5 years and 11 months old. For patients ≥6 and ≤17 years old the CBCL/6-18 is used. An adult version of the checklist, the Achenbach ABCL (ABCL/18-59), is used for patients ≥18 and ≤59 years old.

The CBCL/1½-5 comprises of 100 items, the CBCL/6-18 comprises of 113 items and the ABCL/18-59 comprises of 123 items. Response options are 0=not true; 1=somewhat or sometimes true; 2=very true or often true. Similar items are grouped and summed to produce syndrome scale scores, which are further grouped into problem scales as specified in Table 7. Other scales for CBCL/6-18 and ABCL/18-59 are also derived.

Derivation instructions for the Achenbach scales are given in Appendix 5. For each questionnaire, the individual item responses will not be listed, only the raw scores for the scales given in Table 7 and Table 8 will be listed. For the Achenbach CBCL/1½-5, no scoring will be performed for the language development survey. For the Achenbach ABCL/18-59, no scoring will be performed for the spouse/partner functioning scale or the tobacco, alcohol and drugs substance use scales.

The derived raw scores for the syndrome scales and problem scales as indicated in Table 7, recorded at each visit, will be summarized, on a continuous scale, by questionnaire version and treatment arm. The change from baseline will also be included.

The change from baseline to the end of treatment visit, for the internalizing, externalizing and total problems scales only, will be analyzed for each of the questionnaire versions using the same ANCOVA approach as specified in Section 5.5.3.2.4.

The raw scores for other scales as indicated in Table 8 will also be summarized.

Table 7 Achenbach CBCL and ABCL Syndrome and Problem Scales

Questionnaire Version	Problem Scales	Syndrome Scales
CBCL/1½-5	Internalizing	Emotionally Reactive
		Anxious/Depressed
		Somatic Complaints
		Withdrawn
	Externalizing	Attention Problems
		Aggressive Behavior
	Other	Other Problems
		Sleep Problems

	Total	
CBDL/6-18	Internalizing	Anxious/Depressed
		Withdrawn/Depressed
		Somatic Complaints
	Externalizing	Rule-breaking Behavior
		Aggressive Behavior
	Other	Social Problems
		Thought Problems
		Attention Problems
		Other Problems
	Total	
ABCL/18-59	Internalizing	Anxious/Depressed
		Withdrawn
		Somatic Complaints
	Externalizing	Aggressive Behavior
		Rule-breaking Behavior
		Intrusive
	Other	Thought Problems
		Attention Problems
		Other Problems
	Total	

Table 8 Achenbach CBCL and ABCL Other Scales

Questionnaire Version	Other Scales	Other Sub-Scales
CBDL/6-18	Total Competence	Activities
		Social
		School
ABCL/18-59	Friends	
	Critical Items	

Open-label Extension:

Descriptive summaries described above for the blinded phase will be repeated for OLE visits.

5.5.4.9 Social Communication Questionnaire

Blinded Phase:

The current version of the SCQ will be completed by the caregiver for all patients above the age of 4 years with a mental age of at least 2 years. The scale assesses behavior over the most recent three month period using 40 questions, each to be answered 'yes' or 'no'.

The answer to Item 1 'Is she/he now able to talk using short phrases or sentences?' is not scored and is instead used to determine which of the remaining items relating to abnormal language will contribute to the total score. If the answer to Item 1 is 'yes', then the six items relating to abnormal language will be used and the total score will range from 0 to 39 points from items 2 to 40. If the answer to Item 1 is 'no' then the six items relating to abnormal language will not be used and the total score will range from 0 to 33 points from items 8 to 40 only.

For Items 2, 9, 19 and 20–40, ‘yes’ will be assigned a score of 0 and ‘no’ a score of 1. For all other items, ‘yes’ will be assigned a score of 1 and ‘no’ a score of 0. The total score is calculated by taking the sum of the scores for each item.

In addition to the total score, the following domain scores will be derived:

- Reciprocal Social Interaction: Items 9, 10, 19, 26-33, 36, 37, 39 and 40.
- Communication: Items 2-6, 20-25, 34 and 35.
- Restricted, Repetitive and Stereotyped Patterns of Behavior: Items 7, 8 and 11-16.

The total score and domain scores will be summarized by visit including the change from baseline. The change from baseline for each score will be analyzed using an ANCOVA approach. The model will include baseline and stratified age group as covariates and treatment arm as fixed factor. Sex will also be included as a covariate in the model only if the p-value of the estimate is <0.05.

The estimated least squares means, treatment difference, together with the 95% CIs and p-value will be presented.

The individual responses will not be listed, only the derived information for each derived score will be listed.

Open-label Extension:

Descriptive summaries described above for the blinded phase will be repeated for OLE visits.

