 - 0 if 'None' is ticked.
 - 1 if 1 organization is listed under a, b or c.
 - 2 if 2 organizations are listed under a, b or c.
 - 3 if 3 or more organizations are listed under a, b and c.
- Question III, IIIB
 - Calculated as per IB for the activities scale.
- Question V, V1:
 - 0 if 'None' is ticked.
 - 1 if '1' is ticked.
 - 2 if '2 or 3' is ticked.
 - 3 if '4 or more' is ticked.
- Question V, V2:
 - 0 if 'less than 1' is ticked.
 - 1 if '1 or 2' is ticked.
 - 2 if '3 or more' is ticked.
- Question VI, VIA:
 - For a to c, the below scores will be assigned and then the mean of these scores (excluding blank responses) will be the score for VIA:
 - 0 for "Worse".
 - 1 for "Average".
 - 2 for "Better".
- Question VI, VIB:
 - For item d:
 - 0 if 'Worse' is ticked.
 - 1 if 'Average' is ticked.
 - 2 if 'Better' is ticked.

The school scale is made up of 4 scores and the total score for the school scale is the sum of these 4 scores. If any of the 4 scores are missing or the child does not attend school then the total score for the school scale will not be calculated. The total school score should be rounded to the nearest 0.5. The 4 scores used for the total score for the school scale are derived as follows:

- Question VII, VII1:
 - For a to g, the below scores will be assigned and then the mean of these scores (excluding blank responses) will be the score for VII1:
 - 0 for "Failing".
 - 1 for "Below Average".
 - 2 for "Average".

- 3 for “Above Average”.
- Question VII, VII2:
 - 0 if ‘Yes’ is ticked.
 - 1 if ‘No’ is ticked.
- Question VII, VII3:
 - 0 if ‘Yes’ is ticked.
 - 1 if ‘No’ is ticked.
- Question VII, VII4:
 - 0 if ‘Yes’ is ticked for any academic or other problems in school.
 - 1 if ‘No’ is ticked for any academic or other problems in school.

The total competence score will be calculated as the sum of the activities, social and school scale scores. However, if any of these 3 scales are missing then the total competence score will be set to missing.

ABCL/18–59

The syndrome scale and problem scale grouping of items is shown in Table 16. If data are missing for more than 8 items (not counting items 2, 4, 15, 49, 73, 80, 88, 98, 106, 109, 110 and 123) then the syndrome and problem scales will not be calculated. If items 56a to 56g are missing then they will be scored as 0.

Each of the items is scored 0, 1 or 2 as indicated on the questionnaire. The individual items associated with each syndrome scale are presented in Table 16.

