The syndrome scale scores will be calculated as the sum of the individual items associated with that scale. The problem scale scores will then be calculated as the sum of the corresponding syndrome scale scores as per Table 7 in Section 5.5.4.8. The total problem scale score will be calculated as the sum of the internalizing, externalizing and other problem scales.

Table 16 Syndrome Scale Items for Achenbach ABCL/18–59

Problem Scales	Syndrome Scales	Items
Internalizing	Anxious/Depressed	12, 13, 14, 22, 31, 33, 34, 35, 45, 47, 50, 52, 71, 91, 103, 107, 112, 113
	Withdrawn	25, 30, 42, 48, 60, 65, 67, 69, 111
	Somatic Complaints	51, 54, 56a-i, 100
Externalizing	Aggressive Behavior	3, 5, 16, 28, 37, 55, 57, 68, 81, 86, 87, 95, 97, 116, 118
	Rule-breaking Behavior	6, 20, 23, 26, 39, 41, 43, 76, 82, 90, 92, 114, 117, 122
	Intrusive	7, 19, 74, 93, 94, 104
Other	Thought Problems	9, 18, 36, 40, 46, 63, 66, 70, 84, 85
	Attention Problems	1, 8, 17, 53, 59, 61, 64, 78, 101, 102, 105, 108, 119, 121
	Other Problems	10, 21, 24, 27, 29, 32, 38, 44, 58, 62, 72, 75, 77, 79, 83, 89, 96, 99, 110, 115, 120

The critical items scale score will be calculated as the sum of the following 19 problem items scores:

- 6, 8, 9, 10, 14, 16, 18, 21, 40, 55, 57, 66, 70, 84, 90, 91, 92, 97, 103.

The friends scale is made up of 4 scores and the total score for the friends scale is the sum of these 4 scores. If any of the 4 scores are missing then the total score for the friends scale will not be calculated. The 4 scores used for the total score for the friends scale are derived as follows:

- If 'None' is ticked for item IA then 0 will be used for IB and IC.
- Question I, IA:
 - 0 if 'None' is ticked.
 - 1 if '1' is ticked.
 - 2 if '2 or 3' is ticked.
 - 3 if '4 or more' is ticked.
- Question I, IB:
 - 0 if 'Less than 1' is ticked.
 - 1 if '1 or 2' is ticked.
 - 2 if '3 or 4' is ticked.
 - 3 if '5 or more' is ticked.
- Question I, IC:
 - 0 if 'Not well' is ticked.
 - 1 if 'Average' is ticked.
 - 2 if 'Above average' is ticked.
 - 3 if 'Far above average' is ticked.
- Question I, ID:
 - 0 if 'Less than 1' is ticked.
 - 1 if '1 or 2' is ticked.
 - 2 if '3 or 4' is ticked.
 - 3 if '5 or more' is ticked.

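### The SCQ total is scored on a different item set when the speech answer changes between visits, two SCQ domains have no rule when that answer is 'no', and the ABCL item lists disagree at items 11 and 110

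*SAP*

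**What the plan says.** **SCQ (SAP 5.5.4.9).** Item 1 is not scored. It determines "which of the remaining items relating to abnormal language will contribute to the total score". With 'yes', "the total score will range from 0 to 39 points from items 2 to 40". With 'no', "then the six items relating to abnormal language will not be used and the total score will range from 0 to 33 points", counted on items 8 to 40. The six items concerned are therefore items 2 to 7.

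Three domain scores are also derived. One is "Communication: Items 2-6, 20-25, 34 and 35". The restricted and repetitive domain contains item 7 as well as 8 and 11 to 16. Reciprocal Social Interaction contains none of items 2 to 7.

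On reporting, "The total score and domain scores will be summarized by visit including the change from baseline". Each change score goes into an ANCOVA with baseline as a covariate, and treatment differences and p-values are presented. OLE data are only summarized. Responses to single items are not listed.

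**ABCL/18–59 (SAP Appendix 5).** The scales are not calculated if more than 8 items are missing, "not counting items 2, 4, 15, 49, 73, 80, 88, 98, 106, 109, 110 and 123". In Table 16 the Other Problems scale consists of items "10, 21, 24, 27, 29, 32, 38, 44, 58, 62, 72, 75, 77, 79, 83, 89, 96, 99, 110, 115, 120". Item 11 is on no scale in that table.

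**The concern.** Item 1 asks about present speech, so a caregiver can answer it differently at baseline and at a later visit. The change score is then a difference between a 39-item and a 33-item total. Part of it reflects items entering or leaving the sum rather than any change in behavior. The section gives no common item set, no rescaling and no rule for such patients.

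Two of the three domains contain language items, but the Item 1 rule is written for the total alone. Two programmers could score Communication for a patient without phrase speech out of 8, out of 13, or as missing. This gap affects every patient with a 'no', not only those whose answer changes.

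The SCQ is the only endpoint listed under autistic features (section 3.3.3), and that feature is part of an exploratory objective in both phases (section 2.3). With no listing of single responses and no planned table of Item 1 shifts, a reader of the output may be unable to tell which patients are affected.

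The ABCL matter is a separate bookkeeping discrepancy: two lists in one appendix look as though they should agree, and they differ by one item.

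**Working it through.** **1. The plan's own ranges.** Items 2 to 40: 40 − 2 + 1 = 39. Items 8 to 40: 40 − 8 + 1 = 33. Both stated maxima reproduce, and the difference is 6 items (2 to 7).

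**2. Language items by domain (from the lists in 5.5.4.9).**

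| Score | Items | Language items | Maximum without them |
|---|---|---|---|
| Total | 39 | 2–7 (six) | 33 |
| Communication | 5 + 6 + 2 = 13 | 2–6 (five) | 8 |
| Restricted/repetitive | 2 + 6 = 8 | 7 (one) | 7 |
| Reciprocal Social Interaction | 15 | none | 15 |

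The SAP states the last column only for the total. For the domains it shows what would follow if the exclusion were carried over.

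**3. Effect of a changed answer.** Let C0 and C1 be the scores on items 8 to 40 at baseline and later, and L the score on items 2 to 7 at the visit where they count. Each item scores 0 or 1, so L lies between 0 and 6.

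- 'No' to 'yes': change = (C1 − C0) + L, an artefact of 0 to +6.
- 'Yes' to 'no': change = (C1 − C0) − L, an artefact of 0 to −6.

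That a higher score is more abnormal is inferred from the item coding; the section does not say so.

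Example: with C0 = 15 and a gain of speech, C1 − C0 runs from −15 to +18 and L from 0 to 6. The total change therefore runs from −15 to +24, and it is an improvement whenever items 8 to 40 fall by more than L.

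**4. Effect on an arm mean.** The SAP gives no switching rate, so the rates here are assumptions. Shift in the arm mean = share gaining speech × mean L.

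| Share gaining speech | Largest shift (L = 6) | Shift at mean L = 3 |
|---|---|---|
| 2% | 0.12 | 0.06 |
| 5% | 0.30 | 0.15 |
| 10% | 0.60 | 0.30 |

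Ignoring the baseline adjustment, bias in the treatment difference is approximately the between-arm difference in net switching × mean L. For 10% against 5% at mean L = 3 it is 0.05 × 3 = 0.15 points; at L = 6 it is 0.30. Equal net switching with equal mean L gives 0.

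**5. ABCL lists.** Counting 56a–i as one number, Table 16 holds 18 + 9 + 4 + 15 + 14 + 6 + 10 + 14 + 21 = 111 distinct item numbers with no duplicates. That leaves 123 − 111 = 12 unscored.

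- Unscored in Table 16: 2, 4, **11**, 15, 49, 73, 80, 88, 98, 106, 109, 123.
- Not counted as missing: 2, 4, 15, 49, 73, 80, 88, 98, 106, 109, **110**, 123.

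Eleven of the 12 entries agree. For comparison, the CBCL/1½–5 and CBCL/6–18 tables cover all their items without duplicates.

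**6. What the ABCL mismatch can do.** If the not-counted list is the one in error, the missing-item count is off by at most one (item 11 counted, item 110 not). Only patients at the limit (8 or 9 items counted as missing) can be reclassified. If Table 16 is in error, any scale that should contain item 11 or should not contain item 110, and the Total, is off by 0 to 2 points per item.

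**The case against.** A reader might infer that a patient who gains speech can only score as worse, or that the scoring has the wrong sign. The documents do not support that. Only the contribution of items 2 to 7 runs in one direction, it can be zero, and improvement on the other 33 items can outweigh it.

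A reader might also infer that all the domain scores change their item set. The SAP states no exclusion for any domain, and Reciprocal Social Interaction has no language item. For the other two, the defect is a missing rule.

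On size, it is fair to say that any figure rests on assumed switching, and that only a difference between arms biases the comparison. The ANCOVA concerns 16 weeks of blinded treatment. The longer OLE, where more answers might change, is summarized descriptively. The SCQ is completed only for patients above 4 years with a mental age of at least 2 years, so the youngest children are not in it.

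On the ABCL, scoring an item while leaving it out of the missing count is no contradiction in itself: CBCL items 100, 56h and 113 are treated that way. The evidence of error is the one-for-one mismatch of 110 and 11 in two otherwise identical lists. It does not follow that the Total Problems score is wrong, because the error may lie only in the not-counted list.

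All of this limits the point. It does not supply the missing SCQ rules or reconcile the two ABCL lists.

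**Conclusion.** The point holds at low severity. Followed as written, the SCQ rule gives change scores that are not comparable for patients whose Item 1 answer changes: an artefact of up to 6 points on the total, upward when speech is gained and downward when it is lost. Scoring of Communication and of the restricted/repetitive domain is unspecified for patients with a 'no'. Under the assumed 10% against 5% switching, the treatment difference would move by about 0.15 to 0.30 points of 39. With equal net switching and equal mean contribution it would not move.

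The ABCL lists disagree at items 11 and 110, and the SAP alone cannot show which is right. The effect is confined to patients at the missing-item limit or, if Table 16 is the faulty list, to 0 to 2 points per item on the scales concerned.

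Both scales are exploratory and outside the hierarchy in Table 3 of the SAP, so no confirmatory conclusion depends on them.

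**What to change.** **SCQ.**
- Analyze change from baseline on the items that count for every patient at every visit, at least as a sensitivity analysis: items 8–40 for the total; 20–25, 34 and 35 for Communication; 8 and 11–16 for the restricted/repetitive domain.
- Apply this to all patients. Using the reduced set only where the answer changed would let a post-randomization answer choose the items in the baseline covariate, and would mix 33-item and 39-item scores in one model.
- State how the two affected domains are scored when Item 1 is 'no'.
- Tabulate Item 1 shifts from baseline by arm.

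**ABCL.** Check items 11 and 110 against the scoring form and correct whichever list in Appendix 5 is wrong.

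**Cost.** A few sentences in the SAP, a change to the scoring programs and one extra table; no new data. The price is that the six language items do not contribute to the common-item SCQ analysis.

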5.5 Efficacy Analysis

5.5.1 General Approach

Blinded Phase:

The primary analyses will use the ITT analysis set. Further analyses using the PP analysis set will also be performed for the primary endpoint and secondary endpoints where specified in the sections below.

The primary null hypothesis is:

- Following 16 weeks of treatment there is no difference in effect between the 25 mg/kg/day GWP42003-P treatment arm and the placebo treatment arm in terms of the change in number of TSC-associated seizures during the treatment period compared to baseline.

The null hypothesis will be rejected if there is statistical evidence of a difference between the treatment arms at the α -level of 0.05 for the primary endpoint.

Statistical hypothesis testing will be performed on the primary endpoint and other endpoints as appropriate. Each endpoint, including the primary will have 2 comparisons against placebo (25 mg/kg/day GWP42003-P vs. placebo and 50 mg/kg/day GWP42003-P vs. placebo). Also, 3 key secondary endpoints have been defined.

The primary and key secondary endpoints will be tested with their Type I error controlled by use of a hierarchical gate-keeping procedure, in the sequence given in Table 3. One must reject the null hypothesis of an endpoint at the level of 0.05 (2-sided) to test the hypothesis of the subsequent endpoint in the sequence at the level of 0.05 (2-sided). If a null hypothesis is not rejected then testing will stop and all subsequent analyses will be declared not statistically significant.

Table 3 Hierarchy for Analysis

Test	Endpoint	Treatment Comparison
1	Primary endpoint	25 mg/kg/day GWP42003-P vs. Placebo
2	1 st key secondary endpoint	25 mg/kg/day GWP42003-P vs. Placebo
3	Primary endpoint	50 mg/kg/day GWP42003-P vs. Placebo
4	1 st key secondary endpoint	50 mg/kg/day GWP42003-P vs. Placebo
5	2 nd key secondary endpoint	25 mg/kg/day GWP42003-P vs. Placebo

6	3 rd key secondary endpoint	25 mg/kg/day GWP42003-P vs. Placebo
7	2 nd key secondary endpoint	50 mg/kg/day GWP42003-P vs. Placebo
8	3 rd key secondary endpoint	50 mg/kg/day GWP42003-P vs. Placebo

All statistical tests will be 2-sided and use the 5% significance level.

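### The SCQ analysis lets sex into each ANCOVA only if its p-value is below 0.05, so the covariate set depends on outcome data and can differ between the total score and its three domains

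*SAP*

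**What the plan says.** SAP section 5.5.4.9 (Social Communication Questionnaire) sets up the analysis this way: "The change from baseline for each score will be analyzed using an ANCOVA approach". The fixed part of the model is stated next: "The model will include baseline and stratified age group as covariates and treatment arm as fixed factor". One conditional term follows: "Sex will also be included as a covariate in the model only if the p-value of the estimate is <0.05".

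The same section lists what counts as a score. "In addition to the total score, the following domain scores will be derived", and three domains are then given, so there are four models for the blinded phase. From each model the SAP presents least squares means, treatment differences, 95% confidence intervals and a p-value.

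The section does not say that one decision on sex governs all four scores, or that a model without the condition is also shown. The SAP's other ANCOVAs have fixed covariates and no entry rule of this kind: sections 5.5.2.1, 5.5.3.2.2, 5.5.3.2.4 (whose model is reused for QOLIE-31-P, Vineland-II and Achenbach), 5.5.4.3 and 5.5.4.7. Sex is already collected as a demographic variable (section 5.4.3).

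**The concern.** A covariate that enters on its own significance test makes the final model a function of the outcome. Here the test is applied score by score. The total score could therefore be adjusted for sex while one or more of its domains is not, or the reverse, and the SAP has no rule for reading such results together. A difference between the treatment effect on the total and on a domain would then reflect, in part, a difference in covariates.

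What is at stake is modest: a set of related estimates from one common model that is known before the data are seen. The variable is a baseline characteristic available for every patient, so its role can be settled beforehand. The SAP gives no reason for handling the SCQ differently from its other ANCOVAs.

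**Working it through.** The SAP gives no sample size, power or error rate for the SCQ, so there is no figure of its own to reproduce. The check asks how often the rule would give different covariate sets, and whether it disturbs the treatment test.

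**Inputs from the SAP**
- Threshold for sex: p < 0.05. For tests generally, section 5.5.1 says: "All statistical tests will be 2-sided and use the 5% significance level".
- Model: three arms, baseline, four age groups.
- Scores: 1 total + 3 domains = 4.

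**Inputs assumed** (not in the SAP): 40 to 60 patients per arm with SCQ data, equal numbers of each sex, correlation between scores, and size of any sex effect.

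**Step 1. How the scores are related**
- "Reciprocal Social Interaction: Items 9, 10, 19, 26-33, 36, 37, 39 and 40": 3 + 8 + 4 = 15 items.
- "Communication: Items 2-6, 20-25, 34 and 35": 5 + 6 + 2 = 13 items.
- "Restricted, Repetitive and Stereotyped Patterns of Behavior: Items 7, 8 and 11-16": 2 + 6 = 8 items.
- Sum: 15 + 13 + 8 = 36 of the 39 items (2 to 40) in the total score. Only items 17, 18 and 38 belong to no domain.

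The total is therefore almost the sum of the three domains, and the four decisions on sex cannot be independent.

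**Step 2. Reference value under independence.** With no sex effect, P(at least one model includes sex) = 1 − 0.95⁴ = 0.185. P(sets differ) = 1 − 0.95⁴ − 0.05⁴ = 0.185. Step 1 rules out the independence behind this figure.

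**Step 3. Simulation with correlated scores**

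| Set-up (assumed) | Sex effect | Correlation | P(covariate sets differ) |
|---|---|---|---|
| Total built from the domains, 50 per arm | none | 0.3 to 0.8 | about 0.09 to 0.14 |
| Total built from the domains, 50 per arm | 0.3 SD | 0.5 | about 0.52 |
| Four equally correlated scores, 40 or 60 per arm | none | 0.5 | about 0.16 |
| Four equally correlated scores, 60 per arm | none | 0.8 | about 0.11 |
| Four equally correlated scores, 40 or 60 per arm | 0.2 to 0.4 SD | 0.5 | 0.40 to 0.59 |
| Four equally correlated scores, 60 per arm | 0.3 SD | 0.8 | 0.36 |

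The first set-up is closer to the SCQ. The sets differ most often when sex has a modest real effect, because each model's test then has middling power. With an effect of 0.6 SD and 60 per arm, sex nearly always enters and the sets differ in only about 8% of runs.

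**Step 4. Type I error of the treatment test**
- Total built from the domains: about 0.048 to 0.059 under the rule, against 0.046 to 0.058 with sex always in.
- Four equally correlated scores (4,000 runs per scenario): 0.046 to 0.054 under the rule, against 0.044 to 0.054 with sex fixed in or out. The simulation standard error is √(0.05 × 0.95 / 4000) = 0.0034, so these values cannot be told apart from 0.05.

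**Step 5. Price of always including sex.** With 50 per arm, n = 150. The model without sex has 7 parameters (143 residual degrees of freedom); with sex it has 142.
- If sex has no effect, the loss in variance is roughly 1/142 = 0.7%.
- If sex has an effect of 0.3 residual SD and the sexes are equally frequent, it explains 0.3² × 0.25 = 0.0225 against a residual variance of 1. The residual variance then falls by 0.0225/1.0225 = 2.2%.

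**The case against.** The strongest case for the current text has five parts.

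- **The rule is written down.** It names one covariate and one threshold, leaves the analyst no discretion, and stands in a SAP that section 4 says is approved before the blind is broken. This stands. A reader might infer that the SCQ analysis is not pre-specified; the SAP does not support that. What is left open is the covariate set that results.
- **No inferential damage is shown.** A reader might infer that ignoring the selection step makes the SCQ tests or intervals unreliable. Step 4 found no detectable change in type I error; interval coverage was not examined separately. Arms are randomized, so sex is unrelated to arm apart from chance imbalance, and in a linear model the treatment difference has the same target with or without sex. This stands too.
- **Leaving sex out would also work.** Dropping it from all four models would remove the inconsistency and match the other ANCOVAs. That is true. Including it is preferred because the SAP itself singles sex out as possibly relevant to the SCQ, and step 5 shows little to lose and something to gain.
- **Another data-driven switch remains.** Section 5.5.1 allows non-parametric methods to replace parametric ones if assumptions fail. Fixing sex does not remove that. It does remove the extra switch that only the SCQ has.
- **One decision for all scores could be meant.** The sentence on sex refers to a single model. But the analysis is stated for each score, so a decision per score is the natural reading.

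**Conclusion.** The point holds, and it is minor. The covariate set of each SCQ model depends on the outcome data and may differ between the total and its three domains. With no sex effect this happens in about 9 to 14% of trials, and in about half with a sex effect of 0.3 SD at correlation 0.5. These figures rest on an assumed 50 patients per arm, between-domain correlations of 0.3 to 0.8 in the no-effect case, and a total built from its domains; none of these assumptions comes from the SAP. The 18.5% reference value should not be quoted as the size, since it needs four independent scores.

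The percentages count how often the covariate lists differ. They do not count wrong treatment conclusions. The SCQ is an exploratory endpoint (section 3.3.3) and lies outside the testing hierarchy of Table 3, so no confirmatory claim is touched.

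**What to change.** In section 5.5.4.9, delete the sentence that makes sex conditional on its p-value. State instead that sex is a fixed covariate in all four SCQ models, whatever its p-value, together with baseline, stratified age group and treatment arm. A model without sex can be shown as a sensitivity analysis if wanted.

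This costs one sentence and one degree of freedom per model. It needs no new data, leaves the primary and key secondary analyses alone, and brings the chance that the covariate sets differ to zero. It is a cheap improvement, though not strictly free: precision falls trivially if sex has no effect.
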